Appendix 4.2. Data Quality Assurance

To ensure accurate, complete, and reliable data, Lilly or its representatives will:

- provide instructional material to the study sites, as appropriate
- provide sponsor start-up training to instruct the investigators and study coordinators. This training will provide instruction on the protocol, the completion of the electronic case report forms (eCRFs), and study procedures.
- make periodic visits to the study site
- be available for consultation and stay in contact with the study site personnel by mail, telephone, and/or fax, and
- review and verify data reported to detect potential errors.

In addition, Lilly or its representatives will periodically check a sample of the participant data recorded against source documents at the study site. The study may be audited by Lilly or its representatives and/or regulatory agencies at any time. Investigators will be given notice before an audit occurs.

The investigator will keep records of all original source data. This might include laboratory tests, medical records, and clinical notes. If requested, the investigator will provide the sponsor, applicable regulatory agencies, and applicable ERBs with direct access to original source documents.

Appendix 4.2.1. Data Capture System

The investigator is responsible for ensuring the accuracy, completeness, legibility, and timeliness of the data reported to the sponsor.

An electronic data capture (EDC) system will be used in this study for the collection of CRF data. The investigator maintains a separate source for the data entered by the investigator or designee into the sponsor-provided EDC system. The investigator is responsible for the identification of any data to be considered source and for the confirmation that data reported are accurate and complete by signing the CRF.

Additionally, clinical outcome assessment data (scales, self-reported diary data) will be collected by the subject/investigator site personnel, via a paper source document and will be transcribed by the investigator site personnel into the EDC system.

Data collected via the sponsor-provided data capture systems will be stored at third parties. The investigator will have continuous access to the data during the study and until decommissioning of the data capture systems. Prior to decommissioning, the investigator will receive an archival copy of pertinent data for retention.

Data managed by a central vendor, such as laboratory test data, will be stored electronically in the central vendor's database system and electronic transfers will be provided to the investigator for review and retention. Data will subsequently be transferred from the central vendor to the Lilly data warehouse.

Data from complaint forms submitted to Lilly will be encoded and stored in the global product complaint management system.

Appendix 4.3. Study and Site Closure

Appendix 4.3.1. Discontinuation of Study Sites

Study site participation may be discontinued if Lilly or its designee, the investigator, or the ERB of the study site judges it necessary for medical, safety, regulatory, or other reasons consistent with applicable laws, regulations, and GCP.

Appendix 4.3.2. Discontinuation of the Study

The study will be discontinued if Lilly or its designee judges it necessary for medical, safety, regulatory, or other reasons consistent with applicable laws, regulations, and GCP.

Appendix 4.4. Publication Policy

- The sponsor will comply with the requirements for publication of study results.
- Authorship will be determined by mutual agreement and in line with International Committee of Medical Journal Editors authorship requirements.
- The publication policy for Study I8F-MC-GPIA is described in the Clinical Trial Agreement.

Appendix 4.5. Data Protection

- Participants will be assigned a unique identifier by the investigator. Any participant records or datasets that are transferred to the sponsor will contain the identifier only; participant names or any information, which would make the participant identifiable will not be transferred.
- The participant must be informed that his or her personal study-related data will be used by the sponsor in accordance with local data protection law. The level of disclosure must also be explained to the participant.
- The participant must be informed that his or her medical records may be examined by Clinical Quality Assurance auditors or other authorized personnel appointed by the sponsor, by appropriate IRB/IEC members, and by inspectors from regulatory authorities.

Appendix 4.6. Source Documents

- Source documents provide evidence for the existence of the participant and substantiate the integrity of the data collected. Source documents are filed at the investigator's site.
- Data reported on the CRF or entered in the eCRF that are transcribed from source documents must be consistent with the source documents or the discrepancies must be explained. The investigator may need to request previous medical records or transfer records, depending on the study. Also, current medical records must be available.

Appendix 5. Liver Safety: Suggested Actions and Follow-Up Assessments

Hepatic Evaluation Testing – Refer to protocol Hepatic Safety Monitoring Section 9.4.6.1 for guidance on appropriate test selection.

- The Lilly-designated central laboratory must complete the analysis of all selected testing except for microbiology testing.
- Local testing may be performed in addition to central testing when necessary for immediate patient management.
- Results will be reported if a validated test or calculation is available.

 Results will be reported if a validated test 	or calculation is available.
Hematology	Clinical Chemistry
Hemoglobin	Total bilirubin
Hematocrit	Direct bilirubin
Erythrocytes (RBCs - Red Blood Cells)	Alkaline phosphatase (ALP)
Leukocytes (WBCs - White Blood Cells)	Alanine aminotransferase (ALT)
Differential:	Aspartate aminotransferase (AST)
Neutrophils, segmented	Gamma-glutamyl transferase (GGT)
Lymphocytes	Creatine kinase (CK)
Monocytes	Other Chemistry
Basophils	Acetaminophen
Eosinophils	Acetaminophen protein adducts
Platelets	Alkaline phosphatase isoenzymes
Cell morphology (RBC and WBC)	Ceruloplasmin
Coagulation	Copper
Congulation	Ethyl Alcohol (EtOH)
Prothrombin Time, international normalized ratio (PT-INR)	Haptoglobin
Serology	Immunoglobulin IgA (quantitative)
Hepatitis A Virus (HAV) Testing:	Immunoglobulin IgG (quantitative)
HAV Total Antibody	Immunoglobulin IgM (quantitative)
HAV IgM Antibody	Phosphatidylethanol (PEth)
Hepatis B Virus (HBV) Testing:	Urine Chemistry
Hepatitis B surface antigen (HBsAg)	Drug Screen
Hepatitis B surface antibody (anti-HBs)	Ethyl glucuronide (EtG)
Hepatitis B core total antibody (anti-HBc)	Other Serology

Hepatitis B core IgM antibody Anti-nuclear antibody (ANA)

Hepatitis B core IgG antibody Anti-smooth muscle antibody (ASMA) ^a

HBV DNA ^d Anti-actin antibody ^b

Hepatis C Virus (HCV) Testing: Epstein-Barr Virus (EBV) Testing:

HCV antibody

HCV RNA d

EBV DNA d

EBV DNA d

Hepatitis D Virus (HDV) Testing: Cytomegalovirus (CMV) Testing:

HDV antibody CMV antibody Hepatitis E Virus (HEV) Testing: CMV DNA $^{\rm d}$

HEV IgG antibody Herpes Simplex Virus (HSV) Testing:

HEV IgM antibody
HEV RNA ^d
HSV (Type 1 and 2) antibody
HSV (Type 1 and 2) DNA ^d

Microbiology ^c Liver Kidney Microsomal Type 1 (LKM-1) Antibody

Culture:

Blood Urine

^a Not required if anti-actin antibody is tested.

^b Not required if anti-smooth muscle antibody (ASMA) is tested.

^c Assayed ONLY by Investigator-designated local laboratory ONLY; no central testing available.

^d Reflex/confirmation dependent on regulatory requirements, testing availability, or both.

Appendix 6. Adverse Events: Definitions and Procedures for Recording, Evaluating, Follow up, and Reporting

Appendix 6.1. Special Safety Topics

Appendix 6.1.1. Hypoglycemia

Upon informed consent form (ICF) signing, all participants will be educated about signs and symptoms of hypoglycemia, how to treat hypoglycemia, and how to collect appropriate information for each episode of hypoglycemia.

Hypoglycemia may be identified by spontaneous reporting of symptoms from participants (whether confirmed or unconfirmed by simultaneous glucose values) or by blood glucose (BG) samples collected during study visits. All participants who develop T2DM during the study will be provided with glucometers. Participants without diabetes may, at the investigator's discretion, be given glucometers to assist in the evaluation of reported symptoms consistent with hypoglycemia. Participants receiving glucometers will be provided a diary to record relevant information (for example, glucose values, symptoms).

Hypoglycemic episodes will be recorded on a specific electronic case report form (eCRF) and should not be recorded as adverse events (AEs) unless the event meets serious criteria. If a hypoglycemic event meets severe criteria (see definition below), it should be recorded as serious on the AE and serious AE (SAE) eCRFs, and reported to Lilly as an SAE.

Investigators should use the following definitions and criteria when diagnosing and categorizing an episode considered to be related to hypoglycemia (the plasma glucose [PG] values in this section refer to values determined by a laboratory or International Federation of Clinical Chemistry and Laboratory Medicine blood-equivalent glucose meters and strips) in accordance with the 2019 American Diabetes Association position statement on glycemic targets (American Diabetes Association 2019a):

Glucose Alert Value (Level 1):

- **Documented symptomatic hypoglycemia** is defined as any time a patient feels that he or she is experiencing symptoms and/or signs associated with hypoglycemia, and has a PG level of <70 mg/dL (<3.9 mmol/L).
- **Documented asymptomatic hypoglycemia** is defined as any event not accompanied by typical symptoms of hypoglycemia, but with a measured PG <70 mg/dL (<3.9 mmol/L).
- **Documented unspecified hypoglycemia** is defined as any event with no information about symptoms of hypoglycemia available, but with a measured PG <70 mg/dL (<3.9 mmol/L).

Clinically Significant Hypoglycemia (Level 2):

- **Documented symptomatic hypoglycemia** is defined as any time a participant feels that he or she is experiencing symptoms and/or signs associated with hypoglycemia and has a BG level of <54 mg/dL (<3.0 mmol/L).
- **Documented asymptomatic hypoglycemia** is defined as any event not accompanied by typical symptoms of hypoglycemia but with a measured BG <54 mg/dL (<3.0 mmol/L).
- **Documented unspecified hypoglycemia** is defined as any event with no information about symptoms of hypoglycemia available but with a measured BG <54 mg/dL (<3.0 mmol/L).

Severe hypoglycemia (Level 3):

• Severe hypoglycemia is defined as an episode with severe cognitive impairment requiring the assistance of another person to actively administer carbohydrate, glucagon, or other resuscitative actions. These episodes may be associated with sufficient neuroglycopenia to induce seizure or coma. Blood glucose measurements may not be available during such an event, but neurological recovery attributable to the restoration of BG to normal is considered sufficient evidence that the event was induced by a low BG concentration.

To avoid duplicate reporting, all consecutive BG values ≤70 mg/dL (3.9 mmol/L) occurring within a 1-hour period may be considered to be a single hypoglycemic event (Weinberg et al. 2010; Danne et al. 2013).

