7.7. Concomitant Therapy

Participants will be permitted to use concomitant medications that they require during the study, except certain medications (for example, other medications for weight management) that may interfere with the assessment of efficacy and safety characteristics of the study treatments.

Participants who develop diabetes during the study may initiate medication for glucose control per local standard of care, with the exception of dipeptidyl peptidase-4 (DPP-4) inhibitors or GLP-1R agonists. Initiation of metformin for the treatment of diabetes is permitted, but metformin should not be initiated during the study for the treatment of other metabolic conditions (for example, polycystic ovary syndrome, diabetes prevention).

Investigative site staff will inform participants that they must consult with the investigator or a designated site staff member upon being prescribed any new medications during the study. This may not be possible when initiated for treatment of medical emergencies, in which case, the participant will inform the investigator or a designated site staff member as soon as possible.

Nonstudy medications taken by participants who are screened but not randomized will not be reported to Lilly unless an SAE or AE occurs that the investigator believes may have been caused by a study procedure.

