### **Documented Clinically Significant Hypoglycemia (Level 2):**

- **Documented symptomatic hypoglycemia** is defined as any time a participant feels that he/she is experiencing symptoms and/or signs associated with hypoglycemia and has a BG level of <54 mg/dL (<3.0 mmol/L).
- **Documented asymptomatic hypoglycemia** is defined as any event not accompanied by typical symptoms of hypoglycemia but with a measured BG <54 mg/dL (<3.0 mmol/L).
- **Documented unspecified hypoglycemia** is defined as any event with no information about symptoms of hypoglycemia available but with a measured BG <54 mg/dL (<3.0 mmol/L).

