### **Other hypoglycemia categories:**

• Nocturnal hypoglycemia is defined as any hypoglycemic event that occurs between bedtime and waking.

If a hypoglycemic event meets the criteria of severe, the event would specifically be collected as an SAE. Serious hypoglycemia are defined by pharmacovigilance criteria and will also be captured with an SAE form.

To avoid duplicate reporting, all consecutive hypoglycemic events occurring within a 1-hour period will be considered to be a single hypoglycemic event.

Both the incidence (percent of patients experiencing  $\geq 1$  episode) and the rate (episodes/patient/year) of level 2 or level 3 hypoglycemia, and level 3 hypoglycemia will be reported by treatment group.

[figure not shown]
Severe/serious hypoglycemia will be considered as AESIs. The summaries of severe/serious hypoglycemia will be provided by treatment group. A listing of all events of severe hypoglycemia may be provided, if deemed necessary. This listing will provide treatment allocation, clinical characteristics of the hypoglycemic event, and concomitant antihyperglycemic medications.

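### Between visits, Level 2 hypoglycemia is captured mainly in participants given a meter after randomization, so the by-arm Level 2 or 3 incidence and rate can differ through detection alone

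*Protocol*

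**What the plan says.** **Definition.** Both documents divide Level 2 into symptomatic, asymptomatic and unspecified events, and all three need a glucose value below 54 mg/dL. In Protocol Appendix 6.1.1 the asymptomatic category "is defined as any event not accompanied by typical symptoms of hypoglycemia but with a measured BG <54 mg/dL (<3.0 mmol/L"); SAP 6.13.3.5 repeats the definitions. Level 3 is clinical and can be established without a glucose value.

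**Where glucose values come from.** Appendix 6.1.1 recognizes spontaneously reported symptoms, whether or not confirmed by glucose, "or by blood glucose (BG) samples collected during study visits". The Schedule of Activities places a chemistry panel with glucose at Weeks 12, 24, 36, 44 and 52, at early discontinuation and at Visit 801. Section 9 and Appendix 2 also allow unscheduled or additional tests.

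**Who gets a meter.** Diabetes is an exclusion criterion, so nobody qualifies for a mandatory meter at entry. Later, "All participants who develop T2DM during the study will be provided with glucometers". In addition, "Participants without diabetes may, at the investigator's discretion, be given glucometers to assist in the evaluation of reported symptoms consistent with hypoglycemia". Section 7.7 adds: "Participants who develop diabetes during the study may initiate medication for glucose control per local standard of care", with some drug classes excepted.

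**Analysis.** SAP 6.13.3.5 says that incidence and the rate in episodes per patient per year of "level 2 or level 3 hypoglycemia, and level 3 hypoglycemia will be reported by treatment group". It names no test. The general rules in SAP 6.13 make Fisher's exact test the default for categorical safety responses and use days in the active treatment period as the offset where event rates are modelled. Neither document plans a split by detection source, a summary of meter provision, or a rate per meter-time.

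**The concern.** A Level 2 event is counted only if somebody measures glucose at the time. For most participants that happens on a handful of scheduled days, the first of them at Week 12, although dose escalation starts at Week 0. A participant with a meter can be measured on many more days. The two routes to a meter, incident T2DM and reported symptoms, occur after randomization and could be affected by treatment. The planned rate nevertheless spreads all events over all follow-up, as if capture were uniform.

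At stake is a safety comparison. Hypoglycemic episodes are not recorded as adverse events unless they meet serious criteria (Appendix 6.1.1), so the adverse event tables will not show non-serious Level 2 events. SAP 6.13.3.5 is the only planned summary that uses the 54 mg/dL threshold, and a difference there would naturally be read as a drug effect. A participant who develops T2DM may also start a glucose-lowering drug, and nothing planned identifies Level 2 events that follow. The primary and key secondary efficacy analyses are not affected.

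**Working it through.** The documents give no hypoglycemia rate, no expected number of meters and no testing frequency, so there is no stated figure to reproduce. The check asks how far capture alone can move the by-arm result.

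**Inputs from the documents:** 70 participants per arm; five scheduled on-treatment glucose samples each; Level 2 threshold 54 mg/dL.

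**Share of days with a scheduled sample:** 5 / 364 = 1.4%.

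**Illustration A, counting readings.** Assumptions: the same probability p that any reading is below 54 mg/dL in both arms and from either source; k metered participants in one arm and none in the other; each meter used for 26 weeks.

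- Expected count without meters: 70 × 5 × p = 350p.
- Added by k meters: k × 26 × 7 × p = 182kp for daily readings, or 26kp for weekly readings.
- Ratio: (350 + 182k) / 350 daily, or (350 + 26k) / 350 weekly. p cancels.

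| Meters in one arm (k) | Weekly readings | Daily readings |
|---|---|---|
| 1 | 376/350 = 1.07 | 532/350 = 1.52 |
| 2 | 402/350 = 1.15 | 714/350 = 2.04 |
| 3 | 428/350 = 1.22 | 896/350 = 2.56 |
| 4 | 454/350 = 1.30 | 1078/350 = 3.08 |

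Counting Visit 801 as a sixth reading (70 × 6 = 420) lowers the daily column to 1.43, 1.87, 2.30 and 2.73.

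**Absolute size.** At p = 0.1% and three daily meters, the expected counts are 0.35 and 0.90 events, a difference of 0.55 of one event.

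**Incidence.** Here p does not cancel, because a participant counts once. With three daily meters:

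- At p = 0.1%, the chance of at least one low reading is 1 − 0.999^5 = 0.0050 without a meter and 1 − 0.999^187 = 0.171 with one. The ratio is (67 × 0.0050 + 3 × 0.171) / (70 × 0.0050), about 2.4.
- At p = 1%, the same calculation gives about 1.7.

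**Illustration B, person-time.** Captured rate = λ × [v + m × c × (1 − v)], with the same true rate λ in both arms, v = 5/364, m the share of person-time with a meter, and c the chance of capture while a meter is held. m and c are assumptions.

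| Meter time, placebo vs tirzepatide | Captured rate ratio, tirzepatide/placebo (c = 0.5; c = 1) |
|---|---|
| 5% vs 5% | 1.00; 1.00 |
| 5% vs 10% | 1.64; 1.78 |
| 10% vs 5% | 0.61; 0.56 |
| 5% vs 20% | 2.93; 3.35 |

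Without the visit samples, the three unequal rows would give 2.0, 0.5 and 4.0. Visit sampling therefore dilutes the distortion without removing it. Equal meter time and equal capture give no distortion between arms.

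**The case against.** The strongest reply has five parts.

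1. **Values exist without a meter.** A reader might infer that a participant without a meter can yield a Level 2 value only at the five scheduled samples. The documents do not support that: early discontinuation, Visit 801 and unscheduled tests also supply values, and a symptomatic participant could be tested before Week 12. This stands, and is why the point says mainly.

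2. **Parts of a remedy are already planned.** Level 3 has its own summary. SAP 6.13.6 gives by-visit laboratory summaries and low/normal/high shift tables compared with Fisher's exact test, and glucose is in the chemistry panel. This stands too. But those tables use the laboratory's limits, not 54 mg/dL, and the shift tables include unplanned values.

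3. **Direction is unknown.** It is tempting to say that placebo will have more incident diabetes and tirzepatide more symptom-driven meters. Neither document gives figures for either, and investigators are blinded when they issue discretionary meters. Blinding does not equalize the triggers if treatment affects diabetes onset or symptoms, but no direction can be claimed.

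4. **The size comes from assumptions.** Appendix 6.1.1 sets no testing frequency, and discretionary meters serve to evaluate symptoms. Illustration A also puts every meter in one arm and gives meter and visit readings the same probability of being low. All of that is fair, so the result is a range and not an estimate.

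5. **Counting all events by randomized arm is the stated safety approach.** Correct. Excluding events after T2DM diagnosis or new glucose-lowering medication would condition on a post-randomization event that may itself depend on treatment. Such events should be flagged and kept.

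**Conclusion.** The point holds as a limitation of the planned Level 2 reporting. Certain from the text: Level 2 needs a glucose value, scheduled sampling covers 1.4% of treatment days, meters follow two post-randomization triggers, and the SAP neither separates events by source nor accounts for meter time. It follows that the by-arm Level 2 or 3 incidence and rate can differ without a true difference if meter time differs by arm.

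Whether meter time will differ, in which direction and by how much cannot be determined from the documents. With equal true rates and one to four meters in one arm only, the expected count ratio runs from 1.07–1.30 (weekly readings for 26 weeks) to 1.5–3.1 (daily readings). Absolute counts are small, so a few meters could decide the apparent result.

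A reader might go further and call the hypoglycemia comparison biased, or the whole hypoglycemia analysis unusable. Neither follows: bias between arms needs unequal meter time or capture, which is plausible but not shown, and the separate Level 3 summary does not rest on a glucose value.

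**What to change.** In SAP 6.13.3.5:

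- Keep the planned all-events summary and the separate Level 3 summary.
- Add a by-arm summary of Level 2 values (below 54 mg/dL) from scheduled central-laboratory glucose, which all arms have on the same schedule, and base between-arm statements about Level 2 on it.
- Report meter-detected and unscheduled Level 2 events separately, with the number of participants given meters in each arm and, if the issue date is captured, a rate per meter-time.
- Flag, without excluding, events after T2DM diagnosis or after the start of glucose-lowering medication.

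The cost is SAP wording, one or two extra tables with few events, and possibly one added data item, the meter-issue date. No clinical procedure changes.

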Appendix 6.1.2. Pancreatitis

Acute pancreatitis is defined as an AE of interest in all trials with tirzepatide, including this trial. Acute pancreatitis is an acute inflammatory process of the pancreas that may also involve peripancreatic tissues and/or remote organ systems (Banks and Freeman 2006). The diagnosis of acute pancreatitis requires 2 of the following 3 features:

- abdominal pain, characteristic of acute pancreatitis (generally located in the epigastrium and radiates to the back in approximately half the cases) (Banks and Freeman 2006; Koizumi et al. 2006); the pain is often associated with nausea and vomiting);
- serum amylase (total and/or pancreatic) and/or lipase ≥3x upper limit of normal (ULN)
- characteristic findings of acute pancreatitis on computed tomography (CT) scan or magnetic resonance imaging (MRI).

If acute pancreatitis is suspected, appropriate laboratory tests (including levels of pancreatic amylase and lipase) should be obtained via the central laboratory (and locally, if needed). Imaging studies, such as abdominal CT scan with or without contrast, MRI, or gallbladder ultrasound, should be performed. If laboratory values and/or abdominal imaging support the diagnosis of acute pancreatitis, the participant must discontinue therapy with tirzepatide, but will

continue in the study. A review of the participant's concomitant medications should be conducted to assess any potential causal relationship with pancreatitis.

Each AE of pancreatitis must be reported. If typical signs and/or symptoms of pancreatitis are present and confirmed by laboratory values (lipase or amylase [total and/or pancreatic]) and imaging studies, the event must be reported as an SAE. For a potential case that does not meet all of these criteria, it is up to the investigator to determine the seriousness of the case (AE or SAE) and the relatedness of the event to study drug(s).

Each participant will have measurements of p-amylase and lipase (assessed at the central laboratory) as shown on the Schedule of Activities (Section 2) to assess the effects of the investigational doses of tirzepatide on pancreatic enzyme levels. Serial measures of pancreatic enzymes have limited clinical value for predicting episodes of acute pancreatitis in asymptomatic participants (Nauck et al. 2017; Steinberg et al. 2017a, 2017b). Thus, further diagnostic follow-up of cases of asymptomatic pancreatic hyperenzynemia (lipase and/or pancreatic amylase ≥3x ULN) is not mandated, but may be performed based on the investigator's clinical judgment and assessment of the participant's overall clinical condition. Only cases of pancreatic hyperenzynemia that undergo additional diagnostic follow-up and/or are accompanied by symptoms suggestive of pancreatitis will be submitted for adjudication.

All suspected cases of acute or chronic pancreatitis will be adjudicated by an independent clinical endpoint committee. In addition, AEs of severe or serious abdominal pain of unknown etiology will also be submitted to the adjudication committee to assess for possible pancreatitis or other pancreatic disease. Relevant data from participants with acute or chronic pancreatitis and those with severe or serious abdominal pain will be entered into a specifically designed eCRF page. The adjudication committee representative will enter the results of adjudication in a corresponding eCRF page.

